4.6 PREMATURE TERMINATION OR SUSPENSION OF STUDY

This study may be temporarily suspended or prematurely terminated if there is a sufficiently reasonable cause. Written notification, documenting the reason for study suspension or termination, will be provided by the suspending or terminating party to the principal investigators, the JRCO, ICL and DnaNudge Ltd. If the study is prematurely terminated or suspended, the Trial Manager will promptly inform the JRCO and will provide reason(s) for termination or suspension.

Circumstances that may warrant termination or suspension include, but are not limited to:

- Demonstration of efficacy that would warrant stopping
- Insufficient compliance to protocol requirements
- Data that are not sufficiently complete and/or evaluable

The study may resume once concerns about protocol compliance and data quality are addressed and satisfy the clinical trial team, and ICL.

5 STUDY AGENT(S) AND CONTROL DESCRIPTION

The control arm will receive NICE guidelines for prediabetic individuals via a consultation with a dietitian. The will also receive 2 follow up phone calls from the dietitian during the intervention period, and 2 further follow up phone calls; one to accompany the 12-week clinical measurement, and one to accompany the 26-week final follow up clinical measurement. A further description of the relevant timings of each of the above is given in section 6.2.

The intervention and exploratory arms will receive DNA-based dietary recommendations via consultation with the dietitian. The DNA-based dietary recommendations are determined via the integration of DNA information, scientific nutrigenomic data, and national dietary guidelines. The intervention arm will also have follow-up phone calls with the dietitian as per the control arm, however the exploratory will only receive the app, and no follow-up phone calls.

The DNA of an individual is assessed to determine their genotype for a pre-defined set of SNPs that relate to their metabolism. Their genotype for each SNP is subsequently mapped to the nutrigenetic dietary recommendations in the established database of DnaNudge Ltd., that has intensively reviewed scientific literature to determine the nutrigenomic correlates of each SNP. Furthermore, many of the nutrigenomic links do not act in isolation. Therefore, algorithms have been developed to combine all of the genomic data from the pre-defined set of SNPs to give the optimal, personalised dietary guidelines to each individual.

The genetic analysis will be performed in both the lab in the Centre for Bio-Inspired Technology at Imperial College London, and in a lab-on-chip device called the NudgeBox. The NudgeBox is technology developed by DnaNudge, to miniaturise and improve the speed of genetic analysis techniques such that they can be performed in the NudgeBox, in front of the user, in approximately 15 minutes. It will require the participant to take a buccal cheek swab and insert it into the DNA cartridge provided. The cartridge will contain the primers necessary to analyse metabolism-based SNPs in the saliva sample. The cartridge will then be inserted into the NudgeBox, where the genetic analysis will be performed. This technology will be demonstrated to each participant during their initial consultation with the dietitian.

The exploratory arm will also receive the DnaNudge App to help them with their grocery shopping and food choices. The aforementioned nutrigenetic information for each individual will be supplied in an easy to use electronic format to provide recommendations on demand e.g. via the DnaNudge App or other visual indicator. A summary of the equipment being used is provided in Appendix 3. The user will scan the barcode of a product using the App, which will provide immediate feedback as to whether the food product is good for their health, or is incompatible with one or more of their genetic traits. Furthermore, the App will then link this data to an internal database of food products and produce recommendations of food products that will be very

similar to the first product but more amenable to their genetic traits. Moreover, the App will contain all of the DNA-based dietary recommendations that will have been determined via their DNA in a genetic report. It will also contain educational information on action steps that they can take to improve their health, and how each of their DNA-based guidelines relate to the national dietary guidelines.

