1.2 RATIONALE

The standard treatment protocol for pre-diabetic individuals in the UK is a brief consultation with their clinician highlighting the dangers of an increased risk of diabetes, and some general information regarding healthy eating and the benefits of regular physical activity. The individual will subsequently be contacted every 3 years to assess the state of their glucose regulation (NICE 2012). Despite the implementation of this system, incidence rates of diabetes have continued to rise over the years. From 1994-2011, the number of women diagnosed with diabetes has risen from 1.9 – 4.9%, and 2.9 – 7.0% for men (England 2016). In response to this, the NHS launched the NHS Diabetes Prevention Program (DPP) in 2016. The aforementioned studies and the predictions of the DPP are in agreement that an intensive lifestyle intervention can radically reduce incidence rates of diabetes. However, these interventions are costly, labour-intensive and require the health system to

pre-identify prediabetic patients. The last point is one of the greatest challenges to any diabetes prevention program, as many at-risk individuals will not self-assess to pre-empt a glucose regulation test (Christensen et al. 2004). Our solution aims to assess the improvement in glucose regulation by following a DNA-based diet in comparison with the standard protocol. Furthermore, our intervention will assess whether a positive change can be implemented by using an app to aid in grocery shopping for a DNA-based diet. If effective, this solution could provide a costeffective, widely-distributed, easily scalable prevention tool for improving glucose regulation in high risk individuals. Moreover, the non-invasive nature of the intervention, paired with the autonomy that it provides the individual in choosing their food choices, enables it to be a lowrisk intervention. Furthermore, as a DNA-based diet is relevant for the general public, it has the potential to perform the preventative measures on individuals who do not self-identify as pre-diabetic.

In this pilot study, we propose to use genetic data to guide personalised nutrition in people with impaired glucose tolerance to demonstrate the impact of personalised nutrition on glucose metabolism, anthropometry, non-glucose metabolism and quality of life.

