2.3 EXPLORATORY OBJECTIVES

- To assess the impact of providing DNA-based dietary guidelines via the DnaNudge App, on improving glucose regulation in pre-diabetic individuals
- To assess the impact of providing DNA-based dietary guidelines via the DnaNudge App, on the secondary outcomes outlined in section 2.2.
- To explore the utility of an app as a delivery mechanism for DNA-based dietary advice.
- To examine the changes in leptin measurements via saliva samples during the study.

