6.2.2 FOLLOW-UP

For sample scripts for all interactions with the dietitian for each arm of the study, see Appendices 9 (control arm), 10 (intervention arm), and 11 (exploratory arm).

Visit 4: Initial consultation with a dietitian (Day 0 +/- 6 working days)

- Perform 30-60 minute consultation with the dietitian
- Perform 24-hour recall of food intake for each participant.
- **Intervention and exploratory arms:** Provide NudgeBox experience whereby the participant will provide a buccal cheek swab to perform on-site rapid genotyping. This will provide the participant with a visualisation of how some of their genetic information is analysed

- **Control arm:** Provide NICE guidance by verbal and written communication as per standard care.
- **Intervention arm:** Provide DNA-based dietary information in verbal and written form to participants.
- **Exploratory arm:** Provide DNA-based dietary information via the DnaNudge App.

Visit 5: Follow-up phone-call with the dietitian (Day 14 +/- 6 working days) (Control and intervention arms only)

- Contact participants for a brief phone-call with the dietitian to address any dietary questions/problems.
- Perform 24-hour recall of food intake for each participant.

Visit 6: Glucose regulation review (Day 42 +/- 6 working days)

- Perform clinical assessment of glucose regulation and anthropometric measurements.
 - Obtain urine pregnancy test (if applicable).
 - Collect blood sample (15mL).
 - Assess blood pressure, weight, height, waist circumference, lean body mass, and fat body mass.
 - Perform 0 minutes on 75g glucose OGTT, 120 minutes on 75g glucose OGTT, 120 minutes c-peptide following 75g glucose OGTT, HOMA insulin sensitivity and secretion measurement.
 - Provide saliva sample (2mL) via spit.
- Complete FFQ

Visit 7: Follow-up phone-call with the dietitian (Day 56 +/- 6 working days) (Control and intervention arms only)

- Contact participants for a brief phone-call with the dietitian to address any dietary questions/problems.
- Perform 24-hour recall of food intake for each participant.

Visit 8: Glucose regulation review (Day 84 +/- 6 working days)

- Perform clinical assessment of glucose regulation and anthropometric measurements.
 - Obtain urine pregnancy test (if applicable).
 - Collect blood sample (15mL).
 - Assess blood pressure, weight, height, waist circumference, lean body mass, and fat body mass.

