## **Exploratory analyses**

The first pre-defined exploratory analysis will compare the exploratory arm with the two other arms. More specifically it will test the two following hypotheses: The exploratory arm confers similar or greater benefit compared to the interventional arm and greater benefit compared to the control arm.

The second hypothesis generating exploratory analysis will examine how the changes in leptin measurements correlate with changes in weight overall and by intervention arm. Leptin will be measured via saliva samples at weeks 0, 6, 12 and 26.

The last exploratory analysis will examine how outcomes in the exploratory arm vary across adherence levels. Adherence levels will be defined from the recorded activity of the application.

These analyses are exploratory in nature hence results will be interpreted cautiously.

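### The app arm has no follow-up dietitian calls while the report arm has four, so app versus report compares packages rather than delivery routes, and the SAP's test of similar benefit has no margin

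*Protocol*

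**What the plan says.** Protocol section 5 sets out dietitian contact by arm. For the control arm: "The will also receive 2 follow up phone calls from the dietitian during the intervention period, and 2 further follow up phone calls". For the genetic-report arm: "The intervention arm will also have follow-up phone calls with the dietitian as per the control arm". For the app arm: "the exploratory will only receive the app, and no follow-up phone calls". All three arms have the initial dietitian consultation (Visit 4).

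Sections 6.2.2 and 6.2.3 schedule the calls at Visits 5, 7, 9 and 11 and limit each to two arms, for example "Visit 5: Follow-up phone-call with the dietitian (Day 14 +/- 6 working days) (Control and intervention arms only" and "Visit 7: Follow-up phone-call with the dietitian (Day 56 +/- 6 working days) (Control and intervention arms only". Each call deals with dietary questions and problems as well as taking a 24-hour recall, so it is support and not only data collection. The schedule of events (section 6.2.6) agrees.

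The exploratory objectives (protocol 2.3, repeated in SAP 1.3) concern giving the DNA-based guidelines through the app. One of them reads "To explore the utility of an app as a delivery mechanism for DNA-based dietary advice". The SAP's Study design section separates the three arms only by which guidelines they receive and in what form; it does not mention calls. SAP Exploratory analyses then states the hypotheses to be tested: "The exploratory arm confers similar or greater benefit compared to the interventional arm and greater benefit compared to the control arm". It gives no margin for similarity, and SAP 1.20 sets a 5% significance level for all analyses.

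**The concern.** App versus report is the contrast that would speak to delivery route, because the DNA-based advice is meant to match: section 5 says the app carries the recommendations that the genetic report would hold. But the two arms also differ in follow-up support. Neither protocol 9.5 nor SAP Exploratory analyses names this difference or says how it will be treated in interpretation. A finding that the app does no better, or does worse, could be written up as a finding about app delivery when it may reflect the absence of calls.

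The second problem compounds the first. A test at the 5% level can show a difference but cannot show similarity. With no margin, the plan does not say what result would support the first half of the hypothesis, and a non-significant difference is the likely candidate. The contrast has some reach, because the protocol's Study Summary lists cross-arm differences among all three arms as secondary outcomes.

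**Working it through.** **1. Number of calls.** Section 5 gives 2 + 2 = 4 calls for control, and the same for the report arm. Sections 6.2.2 and 6.2.3 list Visits 5, 7, 9 and 11, which is also 4. The app arm has 0. The two places agree.

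**2. Calls before each measurement**, from nominal days (calls on Days 14, 56, 84 and 182; measurements on Days 42, 84 and 182):

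| Measurement | Calls before it, control and report arms | Accompanying call | App arm |
|---|---|---|---|
| Week 6 (Day 42) | 1 | none | 0 |
| Week 12 (Day 84) | 2 | 1 (Day 84) | 0 |
| Week 26 (Day 182) | 3 | 1 (Day 182) | 0 |

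The imbalance is smallest at week 6 and grows. Under protocol 12.2, calls continue while clinic visits are postponed during a suspension, so more calls may precede a delayed measurement.

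**3. What each contrast contains.**

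- Report versus control (primary): different advice, equal calls.
- App versus report: matched DNA advice, different delivery, and 0 versus 4 calls.
- App versus control: different advice, different delivery, and 0 versus 4 calls.

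If calls help, app versus report estimates the app's delivery effect minus the effect of the calls. The documents give no figure for a call effect, so none is assumed here.

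**4. What a non-significant result would mean.** Inputs:

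- 60 per arm (protocol 9.2, SAP Study design)
- SD 0.6 mmol/L (protocol 9.3 for change from baseline; SAP 1.14 for post-intervention values)
- correlation between baseline and post-intervention values 0.4 to 0.6 (SAP 1.14)
- two-sided 5% level (protocol 9.4)
- a true app deficit of 0.2 mmol/L, chosen for illustration; it is 0.2/0.5 = 40% of the planned difference in protocol 9.3

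Formulas: residual SD after baseline adjustment = 0.6 × √(1 − r²); SE = SD × √(2/n); CI half-width = 1.96 × SE; P(non-significant) ≈ 1 − Φ(0.2/SE − 1.96), the opposite tail being negligible.

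| Analysis, n = 60 per arm | SD | SE | 95% CI half-width | P(non-significant), normal | Same, t distribution |
|---|---|---|---|---|---|
| Unadjusted | 0.600 | 0.110 | 0.215 | 55.3% | 55.9% |
| ANCOVA, r = 0.4 | 0.550 | 0.100 | 0.197 | 48.7% | 49.4% |
| ANCOVA, r = 0.6 | 0.480 | 0.088 | 0.172 | 37.4% | 38.1% |

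For the first row: SE = 0.6 × √(2/60) = 0.110, and 0.2/SE = 1.83 (from the unrounded SE), which is below 1.96. With 50 per arm followed up, the normal approximation gives 61.5% unadjusted (SE 0.120, half-width 0.235) and 45% to 56% with ANCOVA.

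**The case against.** The strongest reply is that leaving out the calls is a disclosed and sensible choice. The background describes earlier programmes as costly and dependent on repeated personal contact, and section 1.2 seeks something cheap and scalable. For that aim, app without calls is the right package to test, and the randomised comparison of packages is valid. This stands, and it is why nothing in the schedule needs to change. But the documents do not say that this package is the question; the objectives and the SAP describe the contrast only by the form in which the advice is given.

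A reader might infer that the app comparisons are uninformative whichever way they fall. The documents do not support that. If calls help, the imbalance works against the app, so a better app result would be conservative. A reader might also infer that app versus control fails to isolate delivery because of the calls. It could not do so even with equal calls, since the advice itself differs. Nor would equal calls make app versus report a pure test of route, because the app adds barcode scanning and product suggestions.

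It is also fair that the app arm has the initial consultation, that only one brief call precedes week 6, that the utility objective draws on app usage data and questionnaires too, and that the SAP labels these analyses exploratory and promises cautious interpretation. That promise does not say what the caution is about. No text says that non-significance will be read as similarity, but no other rule is given.

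**Conclusion.** The point holds within limits. App versus report compares app without follow-up calls against report with follow-up calls, so a null or worse app result cannot be attributed to app delivery. The similar-or-greater hypothesis cannot be established as written: at 60 per arm, a true deficit of 0.2 mmol/L would go undetected in about 55% of trials unadjusted, or about 38% to 49% with the SAP's baseline-adjusted model.

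These figures assume complete follow-up and the planning SD and correlations. They treat the robust regression as being about as efficient as ordinary least squares, and the 0.2 mmol/L is illustrative. They measure the missing margin, not the size of any call effect, which is unknown.

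A reader might extend the point to the primary result. The documents do not support that: report and control have equal calls. Whether dietitian-delivered control advice matches the standard care described in section 1.2 is a separate question. It bears equally on the primary comparison and does not depend on the calls missing from the app arm.

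**What to change.** In protocol 2.3 and 9.5 and in SAP Exploratory analyses:

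- Define the contrasts as the packages delivered: app without follow-up calls versus report with follow-up calls, and app without follow-up calls versus NICE advice with follow-up calls.
- State that a difference, or lack of one, between app and report will not be attributed to the app alone.
- Replace the similar-or-greater test with the estimated difference and its 95% CI, and state that a non-significant difference will not be described as similarity.

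This is a change of wording only. It adds no visits, calls, staff or participants. The cost is a narrower claim for the app: the trial can speak to the package as delivered, not to the delivery route in isolation.

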6 STUDY PROCEDURES AND SCHEDULE

6.1 STUDY PROCEDURES/EVALUATIONS

6.1.1 STUDY SPECIFIC PROCEDURES

The following list of procedures will be performed on all participants:

- Medical history - Participants will be asked a series of questions by the research nurse to ensure that they do not meet any of the exclusion criteria of the study.
- Genetic testing – saliva samples will be provided.
- Physical examination – Assessment of weight, height, waist circumference, blood pressure, lean mass, fat mass.
- Hematology – blood test to examine total cholesterol, HDL cholesterol, LDL cholesterol, fasting triglycerides, HbA1c
- Biological specimen collection – saliva samples will be obtained via the collection of 2ml of spit per sample. Another saliva sample will be provided by means of a buccal cheek swab, to be used in conjunction with the NudgeBox.
- Insulin sensitivity – 0 minutes on 75g glucose OGTT, 120 minutes on 75g glucose OGTT, 120 minutes c-peptide following 75g glucose OGTT, HOMA insulin sensitivity and secretion measurement
- Pregnancy test
- Food frequency questionnaire
- Trial commencement and completion questionnaires

6.1.2 SPECIMEN PREPARATION, HANDLING AND STORAGE

In line with the Human Tissue Act 2004 and the Imperial College London Retention Schedule, the saliva sample will be anonymised, and stored for up to 5 years after study completion. After this time the sample will be destroyed and the data will be kept for up to 10 years after study completion. Blood samples will be stored for 1 year after study completion, upon which time they will be destroyed and the data will be stored for 10 years after study completion.

6.2 STUDY SCHEDULE

6.2.1 SCREENING

Visit 1: Study preparation

- Send participants a Participant Invitation Letter (Appendix 8), and PIS (Appendix 6).
- Schedule a screening visit for potential participants.

Visit 2: Screening (Day -42 to -0 +/-10 working days)

- Discuss the consent procedure (Appendix 5) and any questions that a potential participant may have regarding the trial.

- If the potential participant would like to participate in the trial, they will be provided with an opportunity to sign the consent form and the PIS. A copy of the consent form will be provided to the participant and a copy will be retained by the clinical trial team.
- Review medical history to determine eligibility based on inclusion/exclusion criteria.
- Perform medical examinations needed to determine eligibility based on inclusion/exclusion criteria. This will include a finger prick blood sample that will be analysed either using a point-of-care HbA1c test using a Siemens DCA Vantage POCT device, or a lab analyser, to measure HbA1c levels.
- Send the GP letter (Appendix 7) to the GP of each confirmed participant in the trial who has consented to informing their GP of their participation in the trial.
- Provide participants with access to online and/or hard-copy food frequency questionnaire that they will need to complete for 1 week of food intake prior to their first clinical appointment in the trial (Visit 3).

Following confirmed enrolment in Visit 2, participants will undergo assignment to one of the three arms of the study.

Visit 3: Baseline clinical measurements (Day -21 +/- 10 working days)

- Verify inclusion/exclusion criteria and consent.
- Perform clinical assessment of glucose regulation and anthropometric measurements.
- Obtain urine pregnancy test (if applicable).
- Collect blood sample (15mL).
- Assess blood pressure, weight, height, waist circumference, lean body mass, and fat body mass.
- Perform 0 minutes on 75g glucose OGTT, 120 minutes on 75g glucose OGTT, 120 minutes c-peptide following 75g glucose OGTT, HOMA insulin sensitivity and secretion measurement.
- Provide two saliva samples (2mL each) via spit.
- Complete trial commencement questionnaire.

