3.4 DESCRIPTION OF STUDY DESIGN

Following informed consent, study participants will undergo baseline assessment including assessment of anthropometry, glucose tolerance, metabolism and diet. A trial commencement questionnaire (see Appendix 2) will be completed by each participant upon entry into the trial, and a trial completion questionnaire (see Appendix 4) will be given after 12 weeks of the intervention and after the 26-week follow-up measurement. The questionnaires will address lifestyle factors that may impact the outcomes of the study, and data regarding DnaNudge App utility. DNA will be sampled from saliva from all participants. Two saliva samples will be taken at the baseline assessment (Visit 3 – see [Table 1](#)). One sample will be used to create the DNA-based dietary recommendations and the second sample will be used to assess the leptin levels of the participants. Leptin will be measured from saliva samples taken at the 6-, 12-, and 26-week clinical visits to assess the changes in the hunger hormone during the study. Participants will be

assigned to one of three cohorts using stratified blocked randomisation by age and gender (block size = 15):

1. Control arm (n = 60):

- Participants will receive general health guidelines according to the NICE guidelines, as per standard care.
- Active control

2. Intervention arm (n = 60):

- Participants will receive DNA-based health guidelines via a genetic report (see Appendix 13).

3. Exploratory arm (n = 60):

- Participants will receive DNA-based health guidelines via the DnaNudge App.

The DNA for all arms of the study will be analysed for pre-determined single nucleotide polymorphisms (SNPs) relevant to metabolism. Participants in the intervention arm, will be provided with a hard-copy of a genetic report (for an example report see Appendix 13), which will explain how their SNPs influence their dietary habits. Participants in the exploratory arm, will be given personalised DNA-based dietary advice via the DnaNudge App. Participants in the control arm will be provided with a summary of NICE guidance via a dietitian, as per standard care.

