9.2 THE NUMBER OF PARTICIPANTS

The total number of participants recruited into the study will be 180. All arms of the trial will have 60 participants each.

Participants will be recruited in cohorts of $N = 60$. Each member of a given cohort will be randomly allocated into one of the three arms of the study, as per the blocked randomisation method outlined below. The subdivision of the recruitment process into cohorts has been implemented in order to:

1. Allow sufficient time to perform the genetic analysis to prepare the DNA-based diet for the participants allocated to the intervention and the exploratory arms.
2. Ensure that the data collected is of sufficient quality. If data in the first cohort of 60 participants is not deemed to be of sufficient quality, appropriate changes will be made to ensure that useful data is obtained from subsequent trial participants.
3. To prevent delayed commencement of the study due to recruitment capacity.

Upon enrolment into the trial, each participant will be assigned to a study arm based on stratified, blocked randomisation. A block size of 15 will be employed, using the stratifications and allocation size according to age and gender shown in [Table 2](#).

	Control arm	Intervention arm	Exploratory arm
Women (age <= 40)	5	5	5
Women (age > 40)	5	5	5
Men (age <= 40)	5	5	5
Men (age > 40)	5	5	5

Table 2: Allocation categories and size for the stratified blocked randomisation of participants.

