### **1.8 Baseline characteristics and description of the study population**

Table 1 below lists the baseline variables of interest and presents the methods of derivation. The baseline variables will be summarised for each treatment arm using the mean with standard deviation (sd) for continuous data and count (n) with proportion (%) for categorical data. Statistical testing of between group imbalance in the baseline covariates will not be performed unless required for regulatory or publication reasons. A tabular presentation will be used to display the results.

Table 1. Baseline variables

Description	Definition	Type	Unit	Coding /derivation	CRF
Age		Num	Year	Number of years from date of birth (months : year)	Anonymised Randomisation log
Sex			N (%)		Screening enrolment log
HbA1c		Num	Mmol/mol		Visit2-CRF
Randomisation group	Intervention group assigned at randomization			Anonymised Randomisation log	
Height		m		Visit3-CRF	
Weight		Kg		Visit3-CRF	
Body mass index (BMI)		Kg/m 		Visit3-CRF	
BMI>30		N (%)		Visit3-CRF	
Fat body mass		Kg		Visit3-CRF	
Lean body mass		Kg		Visit3-CRF	
Waist circumference		cm		Visit3-CRF	
Systolic BP		mmHg		Visit3-CRF	
Diastolic BP		mmHg		Visit3-CRF	

Pulse		bpm		Visit3-CRF
Glucose t0	Plasma glucose at time 0 after 75g glucose load	Num	mM/L	Visit3-CRF
Glucose t120	Plasma glucose at 120' after 75g glucose load	Num	mM/L	Visit3-CRF
Insulin t120	Plasma Insulin at 120' after 75g glucose load		IU/L	Visit3-CRF
C-peptide t0	C-peptide at t0 after 75g glucose load		mM/L	Visit3-CRF
Total cholesterol			mM/L	Visit3-CRF
HDL-cholesterol			mM/L	Visit3-CRF
Non-HDL cholesterol			mM/L	Visit3-CRF
LDL cholesterol			mM/L	Visit3-CRF
Fasting TG			mM/L	Visit3-CRF

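### The arm is assigned before the Visit 3 baseline glucose and eligibility check, with no stated time of disclosure; separately, Protocol 4.5 excludes early withdrawals that the ITT set keeps

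*Protocol*

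**What the plan says.** **Time of assignment.** Protocol 6.2.1, after the Visit 2 screening items: "Following confirmed enrolment in Visit 2, participants will undergo assignment to one of the three arms of the study". Protocol 9.2: "Upon enrolment into the trial, each participant will be assigned to a study arm based on stratified, blocked randomisation".

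**What follows assignment.** Visit 3 (nominally Day -21) includes the step "Verify inclusion/exclusion criteria and consent", the first pregnancy test listed in section 6.2, and the oral glucose tolerance test. Visit 2 names only a finger-prick HbA1c, so fasting and 2-hour glucose are first measured at Visit 3. SAP 1.8 takes baseline glucose from the Visit 3 form, and SAP 1.14 puts it in the primary model. The baseline food frequency questionnaire is handed out at Visit 2, and "they will need to complete for 1 week of food intake prior to their first clinical appointment in the trial" (Visit 3). The first arm-specific step is the Visit 4 dietitian consultation.

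**Masking and concealment.** The Study Summary gives masking as none, and SAP 1.4 says that endpoint assessment is not blind. The nearest text to a safeguard is the "Anonymised Randomisation log" named in SAP 1.8, and a remark in Protocol 7.3 that the allocation algorithms were tested for misallocation. Neither says who knows the arm, or from when.

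**Withdrawals.** The last sentence of Protocol 4.5 takes a withdrawn participant out of the study when the time before withdrawal was too short to yield data of use. It sets no minimum time. Protocol 9.1 and SAP 1.6 define the ITT set as everyone randomised. Protocol 9.4 and SAP 1.12 plan multiple imputation by chained equations (MICE), provided nothing contradicts missingness at random.

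**The concern.** Baseline measurement and the final eligibility decision are safest when nobody involved can know the arm. Here both come after assignment, in a trial without masking. If the arm is known by then, three things could differ between arms:

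- whether a participant attends Visit 3;
- how a borderline eligibility finding at Visit 3 is resolved;
- how the participant fills in the baseline food questionnaire.

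At stake is bias in the comparison of intervention with control, not power.

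The sentence in 4.5 raises a related but separate risk. Someone must judge whether a withdrawn participant's data are of use, with no threshold and possibly knowing the arm. If that judgement removes people from the analysis, the analysed set is no longer everyone randomised, and the people removed are also lost to the imputation.

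**Working it through.** **1. Order of steps.** On nominal days, Visit 2 can be as early as Day -42 and Visit 3 is Day -21, so assignment can precede baseline by up to 42 - 21 = 21 days. Section 9.2 does not name Visit 3. It fixes the order only when read with 6.2.1, which ties enrolment to Visit 2.

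**2. Inputs for size.** The plan gives no figure for this bias, so there is none to reproduce. From SAP 1.14: baseline SD 0.7, week 6 SD 0.6, correlation r between 0.4 and 0.6. From Protocol 9.3: target difference 0.5 mmol/L. From both documents: 60 per arm.

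- Slope of week 6 on baseline FPG = r × 0.6/0.7 = 0.343 (r = 0.4) or 0.514 (r = 0.6).
- Residual SD = 0.6 × √(1 − r²) = 0.550 or 0.480.

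**3. Selection on true baseline FPG.** Suppose selective attendance makes true baseline FPG differ by 0.1 mmol/L between arms (assumed). Week 6 FPG then differs by slope × 0.1, which the covariate removes, so the adjusted difference moves by 0. The change-from-baseline model, which SAP 1.9 also plans, has no baseline term and moves by (1 − slope) × 0.1 = 0.066 or 0.049. A simulation with 1,000,000 participants per value of r and no true effect agrees: 0.00 for ANCOVA to two decimals, and 0.067 and 0.048 for the change score.

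**4. Loss related to prognosis beyond baseline FPG.** If k of 60 in one arm are lost, and their adjusted week 6 FPG would have differed by D from those who stay, that arm's mean moves by (k/60) × D. Take D as one residual SD (assumed):

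| k (assumed) | r = 0.4 | r = 0.6 | share of 0.5 |
|---|---|---|---|
| 3 | 3/60 × 0.550 = 0.0275 | 3/60 × 0.480 = 0.024 | 5.5%, 4.8% |
| 6 | 6/60 × 0.550 = 0.055 | 6/60 × 0.480 = 0.048 | 11.0%, 9.6% |

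This is before any imputation and with no offsetting loss in the other arm. For someone lost before Visit 3, SAP 1.8 shows age, sex and Visit 2 HbA1c already collected, so MICE could recover only what these predict.

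**5. Power.** With 50 per arm, the ANCOVA standard error is residual SD × √(2/50) = 0.110 or 0.096, and power for 0.5 exceeds 0.99. Losing a few participants costs almost nothing in power.

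**6. Withdrawals, side by side.** Protocol 9.1 and SAP 1.6 keep every randomised participant, whatever the length of follow-up. The last sentence of 4.5 removes some of them because follow-up was short. A participant randomised at Visit 2 who withdraws in week 2 is in the set under the first rule and may be out under the second. Section 4.5 mentions their earlier data only in connection with reasons for withdrawal. The documents do not say how many people this would affect.

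**The case against.** **Nothing shows that the arm is disclosed early.** This is right. A reader might infer from 6.2.1 that concealment has failed. The documents do not support that: no text places disclosure before Visit 3, the first arm-specific act is at Visit 4, and the appendices were not in the text I had. What stands is that no text rules early disclosure out.

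**Section 3.4 contradicts 6.2.1.** This is tempting, because 3.4 opens with "Following informed consent, study participants will undergo baseline assessment including assessment of anthropometry, glucose tolerance, metabolism and diet" and only later has participants "assigned to one of three cohorts using stratified blocked randomisation by age and gender". But 3.4 is not chronological: it describes 12- and 26-week procedures before it reaches assignment. It does not settle the order. The Randomisation row of Table 1 has lost its column positions in my copy, so I draw nothing from it.

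**The baseline glucose itself would be distorted.** FPG is a blood measurement and no advice is given before Visit 4, so the documents give no specific reason to expect this. Were measured baseline FPG shifted by an assumed 0.1 with no matching week 6 shift, the adjusted difference would move by slope × 0.1 = 0.034 to 0.051.

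**Losses by arm would go unseen.** They would not. SAP 1.7.1 already plans a monthly table of losses and withdrawals by arm. It lacks only a Visit 3 row.

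**Section 4.5 conflicts with other rules too.** Two such readings fail. Listing ineligibility as a ground for discontinuation does not conflict with ITT: a person can stop taking part and still be analysed as randomised, which is ordinary ITT. Nor does 4.5 conflict with 10.2, whose sentence on remaining in the study concerns participants given alternative treatment, not those who withdraw.

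**Exclusion from the study need not mean exclusion from the analysis.** That is possible, and 9.1 and SAP 1.6 are clear. But 4.5 does not draw the distinction, so the conflict depends on the sentence being applied as written.

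**Later assignment leaves little time to prepare advice.** Section 9.2 cites preparation of the DNA-based diet as one reason for recruiting in cohorts. Counting 10 working days as 14 calendar days and 6 as 8, Visit 3 can fall at Day -21 + 14 = -7 and Visit 4 at Day 0 - 8 = -8, so the windows can meet. This is a real cost, but the DNA sample is itself taken only at Visit 3, so the same limit already applies to genotyping.

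**Conclusion.** Both parts hold and should be corrected, with medium confidence.

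**Assignment.** Sections 6.2.1 and 9.2 place it before the eligibility verification, the pregnancy test and the primary covariate, with no stated time of disclosure. This is an avoidable risk of bias, not evidence that bias occurred. Its size is unknown and probably small: 0 in the primary ANCOVA for selection on true baseline FPG, and about 5% of the target for 3 of 60 lost in one arm. That second figure assumes the number lost, a difference of one full residual SD, loss in one arm only, and no recovery through imputation. Visit 2 HbA1c is collected before assignment and is not affected.

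**Withdrawals.** The last sentence of 4.5, applied as written, is incompatible with the all-randomised ITT set and with imputing missing values. Its effect cannot be sized from the documents.

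A reader might also want the arm withheld until after the 24-hour recall at Visit 4. The documents do not support asking for this: 6.2.2 lists the consultation before the recall, and the arm-specific scripts in Appendices 9 to 11 were not available to me.

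**What to change.** **Assignment.** Assign the arm after the Visit 3 measurements and eligibility verification and before Visit 4, and make 6.2.1, 9.2 and Table 1 say so. Genotyping is not delayed, because DNA is sampled at Visit 3 and analysed for all arms. If the order cannot change, state that the arm stays concealed from staff and participants until Visit 3 is complete, and add a row for Visit 3 non-attendance and eligibility failure to the by-arm table in SAP 1.7.1.

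**Withdrawals.** Delete the last sentence of 4.5 and state that data already measured on every randomised participant stay in the ITT analysis and the imputation. This concerns the analysis only; I propose no rule for follow-up after withdrawal.

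**Cost.** Protocol wording and one moved step. Participants who fail at Visit 3 become screen failures, so slightly more people are screened to randomise 180. Where Visits 3 and 4 fall close together, the time to prepare arm-specific advice is short, and scheduling must allow for it.
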